## **12. QUALITY ASSURANCE AND CONTROL**

### **12.1 Data handling and record keeping / archiving**

#### **12.1.1 Case Report Forms**

Data protection and confidentiality are guaranteed and no personal data is presented or published. The signed declaration of consent, as well as the completed questionnaire with the other personal data and demographic and medical personal data are stored in the original as a study document in a locked filing cabinet. The identity of the test persons is encoded in accordance with the encryption (coding) of a person when participating in a research project, as accepted by swissethics. Only a person's year of birth (YYYY) is documented along with a coding number in the CRF. The project manager is responsible for the secure storage of the key for the data encrypted as part of the clinical trial or research project. Direct access to the personal data will continue to be allowed only to authorized persons of the CEC.

#### **12.1.2 Specification of source data and source documents**

The data collected in writing are recorded on paper in the enclosures and are marked as study data. In a double-blind process, the data is transferred from the CRF to an Excel database for the analyses. They are therefore subject to data protection and are regulated in accordance with the provisions set out in chap. 12.1.1.

#### **12.1.3 Archiving of essential clinical investigation documents**

All the documents of the investigation must be archived for a minimum of 10 years after regular or premature termination of the investigation. Data protection will continue to be guaranteed.

### **12.2 Data management**

#### **12.2.1 Data Management System**

The questionnaire for recording physical function is obtained by hand. All other outcomes (joint circumference, range of motion, morphine consumption, VAS scale, length of stay, 10-metre walk test, timed-up-and-go) are noted on the data collection form. Excel is used for further data analysis. Windows Excel will also be used for data pooling and for the graphical representation of the end data. All data is processed on the central research computer. This research computer is located at all times in Landquart (research laboratory). Only the study director and the examiners know the password to unlock this computer. All digital documents are read-only by a password. Only the study director and the examiners know the passwords of the digital documents. The digital documents will be given version numbers. Changes made to the digital documents are saved as a new version number. In addition, all versions will be printed out and signed by the Director of Studies. The printed documents are stored in a separate, lockable filing cabinet. This filing cabinet also contains the password combinations to decrypt the computer and edit the documents. Only the director of studies has the key to this filing cabinet.

### **12.2.2 Data security, access and back-up**

The data is encrypted and treated confidentially, access to the personal data is not allowed to third parties. The digital data collected is stored solely on the institute's own computers and is not passed on to any external persons or to other parties.

Transfer computer. Access to the computers of the research laboratory at the "University of Applied Sciences and Arts Southern Switzerland" is only granted to the head of studies and the examiners as well as persons authorised by the CEC.

### **12.2.3 Analysis and archiving**

After collection, the data is encrypted and stored on another external hard drive for further backup. This is stored in a locked filing cabinet to ensure data protection.

### **12.2.4 Electronic and central data validation**

Immediately after data collection, the quality of the data is checked and verified with the help of the visual representation.

## **12.3 Monitoring**

The collected data can be viewed by authorized persons at any time. Remote monitoring of the study is planned by the following person:

[name], PhD

Vrije Universiteit Brussels

Faculty of Physical Therapy [name]

[name]

[[contact]](mailto:[contact])

Monitoring is regulated in a separate agreement. The monitoring of the study will be carried out externally and virtually (without physical presence). The documents to be checked are made available to the monitor for inspection on a protected page of the Microsoft Teams platform.

## **12.4 Audits and Inspections**

A report on the current status of the study is sent monthly to the study supervisor ([name]. [name]). This also includes demonstrating and presenting results and statistical analyses. An annual report on the course of the study will be submitted to the CEC. Authorized persons of the CEC can view the data forms as well as the digital data on the institute's own computers at any time. Data protection is guaranteed at all times.

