Investigator(s):	
Examiner:          [name] 1,2,3          [name] 1,2,3          [name] 2          [name] 2          [name] 2          [name] 2          1 University College Physiotherapy Thim van der Laan, [name]          2 University of Applied Sciences and Arts Southern Switzerland, Rehabilitation and Exercise Science Laboratory (RESlab), Department of Business Economics, Health and Social Care, Physiotherapy Graubünden, [name]          3 Vrije Universiteit Brussels, Faculty of Physical Education and Physical Therapy, [name]
 
Contact / Principal Investigator:          [name]          University of Applied Sciences and Arts Southern Switzerland          Physiotherapy Graubünden          [name] [name] [name]          [contact]

Investigational Site(s):	
Single-centric investigation:          Regionalspital Surselva AG          [name]          [name]

Statistical considerations:	
Repeated measure ANOVA          Two-way          Bonferroni correction          Factors:          -Task          -Time          The significance level is set at <math>p<0.05</math>, and the statistical data analysis is carried out with SPSS.

Compliance statement:	
This investigation will be conducted in compliance with the CIP, the current version of the Declaration of Helsinki, ISO14155, ICH-GCP (as far as applicable) as well as all national legal and regulatory requirements.

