## **2.8 Early termination of the investigation**

The Sponsor may terminate the investigation prematurely according to certain circumstances, for example:

- ethical concerns,
- insufficient subject recruitment,
- when the safety of the subjects is doubtful or at risk, respectively,
- alterations in accepted clinical practice that make the continuation of the investigation unwise,
- early evidence of benefit or harm of the experimental intervention.

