## **11. STATISTICAL METHODS**

### **11.1 Hypothesis**

Physical Function [AU]

H0: The use of cryotherapy with intermittent dynamic compression has no positive effect on the physical functions of patients after a total knee arthroplasty.

H1: The use of cryotherapy with intermittent dynamic compression has a positive effect on the physical functions of patients after a total knee arthroplasty.

Patient satisfaction [cm]

H0: The use of cryotherapy with intermittent dynamic compression has no positive effect on patient satisfaction of patients after a total knee arthroplasty.

H1: The use of cryotherapy with intermittent dynamic compression has a positive effect on patient satisfaction of patients after a total knee arthroplasty.

Joint circumference [mm]

H0: The joint circumference is not reduced by cryotherapy with intermittent dynamic compression compared to the control group during a hospital stay.

H1: The joint circumference is reduced by cryotherapy with intermittent dynamic compression compared to the control group during a hospital stay.

Skin temperature [C°]

H0: The skin temperature is not reduced by cryotherapy with intermittent dynamic compression compared to the control group during a hospital stay.

H1: The skin temperature is reduced by cryotherapy with intermittent dynamic compression compared to the control group during a hospital stay.

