## 11.2 Determination of Sample Size

A power analysis was performed using the G\*Power App (Düsseldorf, North Rhine-Westphalia, DEU), where a minimum number of 28 subjects was deemed necessary to ensure the statistical power (0.95) to detect a parameter difference at the 5% significance level. The figure below shows the G-Power calculation that was used to determine the sample size.

*Figure 4: Sample Size Calculation*

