### 11.4.2 Primary Analysis

The statistical data analysis will be carried out by [name] after completion of the data collection of the entire project.

Repeated measures analysis of variance (MANOVA) 2

factors:

Factor 1: Intervention (Game Ready vs. Control Intervention)

Factor 2: Time (baseline, 4th postoperative day and 6 weeks)

The significance level is set to  $p < 0.05$ . Statistical data analysis is carried out with SPSS.

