#### **11.4.4 Interim analyses**

The data is processed after the end of the respective subprotocol. Thus, the data analysis for the entire study takes place in stages. No additional interim analyses are planned.

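### The plan puts the analysis after all data collection, yet also allows monthly results, staged analysis and stopping for early benefit, so unadjusted comparative looks at 0.05 are not ruled out

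*Combined protocol and SAP*

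**What the plan says.** Four places in the combined protocol and SAP bear on when outcome data are analysed and who sees the results.

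- Section 11.4.2 (Primary Analysis) has the statistical analysis done "after completion of the data collection of the entire project", with significance at p<0.05.
- Section 11.4.4 (Interim analyses) has data processed as each sub-protocol ends and continues: "Thus, the data analysis for the entire study takes place in stages. No additional interim analyses are planned".
- Section 12.4 (Audits and Inspections) states: "A report on the current status of the study is sent monthly to the study supervisor". On the content of that report it adds: "This also includes demonstrating and presenting results and statistical analyses".
- Section 2.8 (Early termination) gives, among its example reasons for the sponsor to stop, "early evidence of benefit or harm of the experimental intervention".

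The sample size in section 11.2 is set "at the 5% significance level", with no mention of repeated testing. The synopsis lists a "Bonferroni correction" without saying what it covers, and section 11.4.2 does not repeat it. Nowhere is there a schedule of looks, a stopping boundary, a division of alpha, or a statement that the monthly results are pooled over arms.

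**The concern.** Sections 11.4.2 and 12.4 cannot both be followed literally while data are being collected: an analysis that is run only at the end cannot appear in monthly reports before the end. Section 2.8 presupposes that somebody may see efficacy evidence early, and section 11.4.4 leaves room for it.

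If any of those reports compares Game Ready with control, it is an efficacy look without a stopping rule. A final p<0.05 would then no longer carry a 5% error rate, and a reader could not tell whether it came from the only look or the last of many. With 28 subjects, early estimates are also unstable, so a chance early difference is likely to look large. Participants and the person operating the device know the allocation, and some outcomes, such as KOOS and the pain scale, are self-reported. That is a further reason to keep emerging differences out of circulation.

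**Working it through.** **1. The passages side by side**

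| Section | Timing of analysis | Comparative looks before the end? |
|---|---|---|
| 11.4.2 | once, after all data collection | no |
| 11.4.4 | staged, by sub-protocol; none beyond that | unclear |
| 12.4 | monthly, to the study supervisor | not excluded |
| 2.8 | stopping for early benefit possible | presupposed |

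The primary analysis in 11.4.2 compares the two arms. The secondary analysis in 11.4.3 compares an intervention side with a control side. No analysis pooled over arms is described.

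**2. The plan's own basis**

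The figure of 28 subjects (14 per group) with power 0.95 is reproduced by a repeated-measures MANOVA interaction, 2 groups by 3 times, with effect size f(V)=0.8, noncentrality 0.8² × 28 = 17.92, df (2, 25) and alpha 0.05. The power is 0.955. The type of effect size is an assumption, because the G*Power figure is not shown. That calculation is for one test at 0.05.

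**3. How many looks there could be**

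The documents give no number, so a range is needed.

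- Upper end: the synopsis plans first subject in for May 2022 and last out for June 2023, about 13 monthly reports.
- Lower count: the plan is dated 21.06.2022, and section 11.4.1 admits only complete data sets, so nobody counts until the 6-week visit. Assume a July 2022 start and even accrual. Complete data then arrive from mid-August to the end of June, about 10.5 months, at 14 / 10.5 = 1.33 per arm per month. Three per arm takes 3 / 1.33 = 2.3 months (end of October) and four takes 3.0 months (mid-November). Month-end reports from October or November to June give 9 or 8 looks.

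**4. Type I error for one outcome**

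With no true effect and K equally spaced looks, the statistic at look k is Z_k = (X_1 + … + X_k)/√k with independent standard normal X. The error is P(|Z_k| > 1.96 for at least one k ≤ K). This was simulated (400,000 runs), as were two-sample t tests on data accumulating to 14 per arm (at least 60,000 runs).

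| Looks | Normal statistic | t tests ending at 14 per arm |
|---|---|---|
| 1 | 0.050 | 0.049 |
| 2 | 0.083 | 0.083 |
| 5 | 0.141 | 0.146 |
| 8 | 0.177 | 0.173 (first look at 3 per arm), 0.157 (at 4) |
| 9 | 0.185 | 0.178 (at 3), 0.163 (at 4) |
| 12 | 0.207 | 0.188 (at 3) |
| 13 | 0.215 | 0.214 (at 2) |

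The plan does not say whether the test is one- or two-sided. The hypotheses are directional (for example, that treatment "has a positive effect on the physical functions of patients after a total knee arthroplasty"). One-sided at 0.05, 13 looks give 0.189.

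**5. After the fix**

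One final comparison returns 0.05. Had 12 or 13 comparative looks been wanted, a constant nominal level of about 0.010 or 0.009 per look (Pocock type) would be needed to hold 0.05 overall.

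**The case against.** The strongest reply is that a consistent reading exists. Section 11.4.2 fixes the analysis at the end, the investigation schedule places statistics after data collection, and the investigation runs to December 2024. The monthly reports could therefore present analyses only once they exist. Section 12.4 does not say that results are shown by arm, and pooled results would not inflate the error. All of this stands as a possible reading, but the text neither states it nor excludes the other one.

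Several stronger inferences are tempting, and the documents do not support them:

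- *That the plan flatly denies interim analyses.* Section 11.4.4 says only that no further ones are planned beyond the staged processing. The stages are tied to sub-protocols, which section 9.2 places in the visit log of 9.1. They may be visits or tests rather than repeated tests of one accumulating comparison. The text is ambiguous rather than contradictory on this point.
- *That every statistical analysis compares the arms.* The secondary analysis in 11.4.3 is worded as a comparison of sides.
- *That the trial is open to staff.* Section 6.2.2 blinds the examiners and the statistician. Of the study staff, only the device operator must know the allocation. Blinding does not settle the matter, however: coded arms can still be compared and a p-value reported.
- *That the monthly report drives stopping.* It goes to the study supervisor, whereas 2.8 gives termination to the sponsor. No section says that the report reaches the sponsor, and the reasons in 2.8 are only examples.
- *That the error rate is about 20%.* That is the upper end, and it needs by-arm testing of the same outcome at nearly every report and a trial that could stop at any crossing. The documents state neither.

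The number of primary outcomes is a separate multiplicity question and does not enter these figures.

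**Conclusion.** The inconsistency is real and lies in the current text. Sections 2.8, 11.4.2, 11.4.4 and 12.4 together permit comparative looks during the trial, while the test stays at 0.05 with no boundary, alpha adjustment or pooled-only restriction. That is a gap in what the plan permits, not evidence that such looks are intended or that they would lead to stopping.

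The size depends on two assumptions that the documents do not state: that reports compare the arms on one outcome at two-sided 0.05, and that a crossing could be acted on. On those assumptions the error is about 8% for 2 looks, 14% for 5, 17 to 19% for 8 or 9 (16% by t test if the first look waits for four per arm), and up to about 21% for 13. If the reports are pooled, or no comparison is made before the end, it stays at 5%.

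**What to change.** - **Section 12.4:** before database lock, limit the monthly report to recruitment, visit completion, data quality and adverse events, with no comparative outcome results.
- **Section 11.4.4:** replace the staged-analysis wording with one final comparative analysis after the last 6-week visit, matching 11.4.2. Checking and processing data as visits finish can continue.
- **Section 2.8:** reconcile the early-benefit reason with this, since no analysis would then supply such evidence. Either drop that reason, or prespecify the look, its boundary and who receives the result. Leave the safety and harm reasons unchanged.

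The cost is wording in three sections. It needs no extra subjects, visits or measurements. The one loss is that the supervisor no longer sees efficacy results early.

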## **12.5 Confidentiality, Data Protection**

The examiners ensure that the privacy of the participants is maintained. In particular, data protection and confidentiality are guaranteed and no personal data is presented or published. The signed declaration of consent, as well as the completed questionnaire with the other personal details, are kept in the original as a study document in a locked filing cabinet. The data is encrypted and treated confidentially, access to the personal data is not allowed to third parties. The digital data collected is stored solely on the institute's own computers and is not passed on to any external persons or transferred to other computers. Direct access to the personal data is only allowed to authorized persons of the CEC.

## **13. PUBLICATION AND DISSEMINATION POLICY**

The examiners ensure that the privacy of the participants is maintained. In particular, the data protection and confidentiality of the data are guaranteed and no personal data is presented or published nor passed on to outsiders and unauthorized persons.

## **14. FUNDING AND SUPPORT**

### **14.1 Funding**

The study is funded by the University of Applied Sciences and Arts Southern Switzerland, Physiotherapy Graubünden. The auditors are employed by this institute and are remunerated for their work on this study in accordance with their employment contracts. No further financial support is needed.

### **14.2 Other Support**

The Game Ready GRPro 2.1 thermotherapy device is kindly provided by the Swiss distributor MTR Health & Spa AG for the entire duration of the study. There is no written agreement. However, no obligations have been entered into towards the company and the independence of data analysis and discussion is thus guaranteed. **MTR Health & Spa AG**

[name]

[name]

[contact]

[contact]

## **15. INSURANCE**

There is a business liability insurance with Baloise Insurance for Thim van der Laan AG in Landquart. Any damage in connection with the research activities at the Regionalspital Surselva AG is covered by the public liability insurance of the Regionalspital Surselva AG. A confirmation is attached to this application.

## 17. APPENDICES

2. *Subject Information Declaration of Consent*
3. *Data collection form*
4. *Copy of proof of insurance*
5. *Advertisement*
6. *Protocol Synopsis*
7. *Employee*
8. *CV's Investigator and Sponsor*
9. *GCP Proof Investigator and Sponsor*

9. Operating manual and CE certification GR PRO 2.1
